17.3. Reporting of Adverse Events

17.3.1. Adverse Events and Device Deficiency Classification

All reported AEs and DDs will be reviewed by a Medtronic representative. Adverse Events will be classified according to the definitions provided.

Upon receipt of AEs at Medtronic, a Medtronic representative will review the AE/DD for completeness and accuracy and when necessary will request clarification and/or additional information from the Investigator. Medtronic will utilize the Medical Dictionary for Regulatory Activities (MedDRA), to assign a MedDRA term for each AE based on the information provided by the investigator.

Regulatory reporting of AEs and DDs that could have led to an SADE will be completed according to local regulatory requirements. Refer to Table 14 for a list of required investigator and Medtronic reporting requirements and timeframes. It is the responsibility of the investigator to abide by any additional AE reporting requirements stipulated by the IRB/EC responsible for oversight of the study.

APPENDIX 1 contains the Foreseeable Adverse Event List (FAL), which is a list of adverse events related to the system or procedure that have been observed in previous studies and may be experienced by subjects. This list may help to assess if an AE is unanticipated in nature.

For emergency contact regarding a UADE, SAE and/or SADE, contact a Attain Stability Quad Clinical Study representative immediately (refer to the study contact list provided in the site's study documents binder/investigator site file or refer to the Sponsor Contact Information section provided in the CIP).

Adverse Events and Deaths will be classified according to the standard definitions as outlined below:

Table 13: Adverse Event Classification Responsibilities

What is classified?	Who classifies?	Classification Parameters

Relatedness	Investigator	Device, RA Lead, RV Lead, LV Lead, Implant Tool(s), Programmer, Procedure, Cardiovascular, Heart Failure, MRI
	Sponsor	Device, RA Lead, RV Lead, LV Lead, Implant Tool(s), Programmer, Procedure
Seriousness	Investigator	SAE
	Sponsor	SAE, UADE/USADE, Device Deficiency with SADE potential
Diagnosis	Investigator	Based on presenting signs and symptoms and other supporting data
	Sponsor	MedDRA term assigned based on the data provided by Investigator
Death Classification	Investigator	Sudden Cardiac, Non-sudden Cardiac, Non-Cardiac, Unknown

An independent Clinical Events Committee (CEC) will review and adjudicate, at a minimum, all events classified by the investigator or Medtronic as procedure or system related to determine relatedness and complication or observation classifications. In addition, the CEC will also review and adjudicate all Adverse Events resulting in death.

17.3.2. Adverse Events and Device Deficiency Reporting Requirements

Regulatory reporting of AEs and device deficiencies will be recorded and reported according to local regulatory requirements. It is the responsibility of the Investigator to abide by the adverse event reporting requirements stipulated by local law and the site's IRB/EC.

Table 14: Reporting Requirements

Serious Adverse Events (SAEs)	
Investigator submit to:	
Medtronic	
Canada: Investigators are required to report SAEs to the sponsor immediately except for those SAEs that the protocol or other document (e.g. Investigator's Brochure (IB)) identifies as not needing immediate reporting. The immediate reports should be followed promptly by detailed, written reports.
 
Medical Devices Regulations, sections 59-61. A guidance for "immediately" is within 72 hours of the investigator becoming aware of the event; Report to sponsor, without unjustified delay ISO 14155:2011, sec 9.8.b).
 
EMEA: Immediately after the investigator first learns of the event or new information in relation with an already reported event.
 
All geographies: Report to the sponsor, without unjustified delay, all serious adverse events.

Regulatory authorities	All geographies: Submit to regulatory authority per local reporting requirement.
Ethics Committee	All geographies: Submit to Ethics Committee per local reporting requirement.
Sponsor submit to:	
Regulatory authorities	All geographies: Submit to regulatory authority per local reporting requirement.

Ethics Committee	All geographies: Submit to Ethics Committee per local reporting requirement.
Adverse Device Effects (ADEs),	
Investigator submit to:	
Medtronic	EMEA: Immediately after the investigator first learns of the event or new information in relation with an already reported event. All geographies: Submit in a timely manner after the investigator first learns of the effect.
Regulatory authorities	All geographies: Submit to regulatory authority per local reporting requirement.
Ethics Committee	All geographies: Submit to Ethics Committee per local reporting requirement.
Sponsor submit to:	
Regulatory authorities	All geographies: Submit to regulatory authority per local reporting requirement.
Ethics Committee	All geographies: Submit to Ethics Committee per local reporting requirement.
Serious Adverse Device Effects (SADEs), Unanticipated Adverse Device Effects (UADEs), Unanticipated Serious Adverse Device Effects (USADEs),	
Investigator submit to:	
Medtronic	US: Submit as soon as possible, but no later than within 10 working days after the investigator first learns of the event. (21 CFR 812.150(a)(1)) Canada: SADEs on the patient, the user or any other person must be reported to the Sponsor within 72 hours after it comes to the attention of the qualified investigator. It is recommended for the investigator to report safety events as soon as possible but no longer than 15 calendar days." All geographies: Immediately after the investigator learns of the event or of new information in relation to an already reported event.
Regulatory authorities	All geographies: Submit to regulatory authority per local reporting requirement
Ethics Committee	All geographies: Submit to Ethics Committees per local reporting requirement.
Sponsor submit to:	
Regulatory authorities	All geographies: Submit to regulatory authority per local reporting requirement.
Ethics Committee	All geographies: Submit to Ethics Committee per local reporting requirement.
Investigators	All geographies: Submit per local reporting requirement.
All other reportable Adverse Events	
Investigator submit to:	
Medtronic	All geographies: Submit in a timely manner after the investigator first learns of the event.

Regulatory authorities	All geographies: Submit to regulatory authority per local reporting requirement.
Ethics Committee	All geographies: Submit to Ethics Committee per local reporting requirement.
Device Deficiencies with SADE potential	
Investigator submit to:	
Medtronic	
Canada: DDs that have resulted in any of the consequences characteristic of an SAE on the patient, the user or any other person or could do so were it to reoccur must be reported to the Sponsor within 72 hours after it comes to the attention of the qualified investigator
 
EMEA: Immediately after the investigator first learns of the deficiency or of new information in relation with an already reported deficiency.
 
All other geographies: Submit or report as required per local reporting requirements.

Regulatory authorities	All geographies: Submit to regulatory authority per local reporting requirement.
Ethics Committee	All geographies: Submit to Ethics Committee per local reporting requirement.
Sponsor submit to:	
Regulatory authorities	All geographies: Submit to regulatory authority per local reporting requirement.
Ethics Committee	All geographies: Submit to Ethics Committee per local reporting requirement.
All other Device Deficiencies	
Investigator submit to:	
Medtronic	All geographies: Submit in a timely manner after the investigator first learns of the deficiency.
Regulatory authorities	
Canada: any DD that:
 
 a. has resulted in any of the consequences characteristic of an SAE on the patient, the user or any other person; These must be reported by Medtronic to the Regulator within 10 days from the date Medtronic becomes aware. or b. could do so were it to reoccur. These must be reported by Medtronic to the Regulator within 30 days from the date Medtronic becomes aware. 
All geographies: Submit to regulatory authority per local reporting requirement.

Ethics Committee	All geographies: Submit to Ethics Committee per local reporting requirement.

17.4. Subject Death

17.4.1. Death Data Collection

All subject deaths must be reported by the investigator to Medtronic on an AE form (AE with outcome of death) as soon as possible after the investigator first learns of the death. In case of death, there should be one SAE with the outcome of death reported.

In the event of a subject's death, it is recommended that the implanted system be explanted and returned to Medtronic for analysis whenever possible per local process. Local laws and procedures must be followed where applicable.

System Interrogation Data Recommendations:

- After the subject has died but prior to explant, it is strongly recommended that the system be interrogated and a full summary interrogation (Interrogate All) performed when possible, and saved in a digital format (Save-to-Media). Store one copy of the save-to-media at the site and send a copy to Medtronic.
- Make the device interrogation/save-to-media file before any programming to prevent overwriting information in the device's memory and/or distinguishing between events detected during versus before the explant procedure.
- Recommend obtaining the exact date and time of death as lower temperatures after death can cause ERI and other "event flags" to be stored in the device memory.

If the system is not interrogated, an explanation must be entered on the AE form. For ICD systems, the ventricular tachycardia (VT) and ventricular fibrillation (VF) detection capabilities must be disabled to avoid inadvertent shocks. If any system component is returned to Medtronic, internal return product reporting systems may be used to gather additional information about the returned device/component.

A copy of the death certificate, if available and allowed by state/local law, should be sent to the Medtronic Attain Stability Quad Clinical Study team. When a death occurs in a hospital, a copy of the death summary report and all relevant hospital records should be sent to the Medtronic Attain Stability Quad Clinical Study team, if available. If an autopsy is conducted, the autopsy report should also be sent to the Medtronic Attain Stability Quad Clinical Study team if available and allowed by state/local law. When the death occurs at a remote site, it is the investigative site's responsibility to attempt retrieval of information about the death. Additionally, device disposition information should be updated. In summary, the following data will be collected:

- Date of death
- Detailed description of death
- Cause of death
- Relatedness to system and/or procedure
- Device interrogation and Save-to-Media (if available)
- Device disposition information
- Death summary/hospital records (if available and allowed by state/local law)
- Autopsy report (if available and allowed by state/local law)
- Death certificate (if available and allowed by state/local law)

17.4.2. Death Classification and Reporting

Sufficient information will be required in order to properly classify the subject's death. The Investigator shall classify each subject death per the following definitions:

Cardiac Death: A death directly related to the electrical or mechanical dysfunction of the heart.

Sudden Cardiac Death (SCD): Natural death due to cardiac causes, indicated by abrupt loss of consciousness within one hour of the onset of acute symptoms; preexisting heart disease may have been known to be present, but the time and mode of death are unexpected. If time of onset cannot be

determined, SCD will alternatively be defined as any unexpected cardiac death occurring out of the hospital or in the emergency room as dead on arrival.

Non-sudden Cardiac Death: All cardiac deaths that are not classified as sudden deaths, including all cardiac deaths of hospitalized subjects on inotropic support.

Non-cardiac Death: A death not classified as a cardiac death.

Unknown Classification: Unknown death classification is intended for use only when there is insufficient or inadequate information to classify the death.

Table 15: Subject Death Classification Responsibilities

What is classified?	Who classifies?	Classification Parameters
Death Classification	Investigator	Sudden Cardiac, Non-sudden Cardiac, Non-cardiac, Unknown

The Clinical Events Committee will review all deaths and provide a final adjudication of the death classification.

Regulatory reporting of Subject Deaths will be completed according to local regulatory requirements.

17.5. Product Complaint Reporting

Product complaint reporting and vigilance reporting are applicable and AEs related to any market-released device during the study must be reported. The reporting of product complaints is not part of the Attain Stability Quad Clinical Study and should be done in addition to the AE reporting requirements. Refer to local regulations for reporting requirements.

Product Complaint: Any written, electronic or oral communication that alleges deficiencies related to the identity, quality, durability, reliability, safety, effectiveness or performance of a medical device that has been placed on the market.

- Abuse: Abnormal use (definition acc. #4.1 of Meddev 2.12-1 rev8)
- Misuse: Use error (definition acc. #4.20 of Meddev 2.12-1 rev8)

It is the responsibility of the investigator to report all product complaint(s) associated with a medical device distributed by Medtronic, regardless whether they are related to intended use, misuse or abuse of the product. Reporting must be done immediately and via the regular channels for market-released products. The reporting of product complaints by the clinical team must be done according to the local Standard Operating Procedures. Medtronic will notify the regulatory authorities (e.g. Competent Authority) as applicable for the following incidents immediately upon learning of them:

- Any malfunction or deterioration in the characteristics and/or performance of a device, as well as any inadequacy in the labeling or instructions for use which led or might have led to the death or serious deterioration in the state of health of a patient, user, or other person.
- Any technical or medical reason resulting in withdrawal of a device from the market by the manufacturer.
- Any serious deterioration in the state of health, including:
 - Life-threatening illness or injury
 - Permanent impairment of a body function or permanent damage to a body structure

- A condition necessitating medical or surgical intervention to prevent permanent impairment of a body function or permanent damage to a body structure

18. Data Review Committees

18.1. Clinical Events Committee

The study will utilize a Clinical Events Committee (CEC). At regular intervals, an independent CEC will review events and adjudicate at a minimum all system, and procedure-related events. Additionally, the CEC will provide an adjudication of the death classification for all reported deaths.

The CEC will consist of a minimum of three (3) non-Medtronic-employed physicians that are not participating investigators for the study, including a CEC chairperson.

Medtronic personnel may facilitate and participate in CEC meetings but will be non-voting members.

For AEs and deaths reviewed by the CEC, Medtronic will provide the CEC with the Investigator's description and classification and supportive documentation (when available). The CEC is responsible for reviewing the Investigator's assessment and supportive documentation (when available), reviewing applicable definitions, and determining final classifications for all adjudication parameters. For AEs, classification includes system/procedure relatedness and complication or observation. Additionally, the CEC will provide an adjudication for all reported deaths, including system/procedure relatedness and cardiac relatedness.

If the CEC disagrees with the investigator's classification of the event, the difference will be provided to the investigator. If the investigator agrees with the CEC's adjudication, the CRF documenting the AE will be updated accordingly.

If the investigator does not agree with the CEC's adjudication classification, both determinations will be provided within the final report; however the CEC's adjudication will be used for data analysis. The disagreement will also be included in reporting to ethics committees and regulatory authorities, if required.

18.2. Data Monitoring Committee

A Data Monitoring Committee (DMC) will not be utilized for this study considering:

- An independent CEC will be formed to adjudicate at minimum all system and procedure related events and all deaths.
- This study does not meet FDA's recommended criteria (Guidance for Clinical Trial Sponsors: Establishment and Operation of Clinical Trial Data Monitoring Committees) for when a study should use a DMC, primarily because the study is not evaluating the effectiveness of a treatment intended to prolong life or reduce the risk of a major adverse health outcome.
- As a result of risk analysis and mitigation efforts as outlined in Section 16, any residual risk associated with this study is considered low and acceptable.
- The Attain Stability Quad MRI SureScan LV Lead (Model 4798) is a modification of the currently market approved Attain Performa lead Models 4298, 4398, and 4598 is a modification of the currently market approved Model 4396 LV lead. The Attain Stability Quad lead Model 4798 has a similar electrode spacing as the Attain Performa lead Models 4298, 4398, and 4598.
- Study will be conducted under FDA oversight via an investigational device exemption (IDE).

19. Statistical Design and Methods

This section presents statistical considerations for the study design and provides a high-level description of planned analysis and reporting. More details will be given in a separate Statistical Analysis Plan (SAP) that will be completed before data freeze for the primary objective analysis. Any deviation to the pre-specified statistical analyses will be noted in the study report. The analysis of the study objectives will be completed when the sample size requirements (see Table 18) for all the study primary and secondary objectives are met. An interim analysis will be conducted when 360 subjects are enrolled in the study. This interim analysis is specifically designed for one of the secondary objectives (details in Section 19.2.2).

19.1. Primary Objectives

19.1.1. Primary Safety Objective

Objective

The Attain Stability Quad MRI SureScan LV Lead (Model 4798) will be considered safe if the probability of subjects free of Model 4798 lead-related complications at 6 months post-implant is greater than 87% (i.e., the lower bound of a one-sided 97.5% confidence interval must be greater than 87%).

Hypothesis:

$$H_0: S_{(6\text{-month})} \leq 87\%$$

$$H_1: S_{(6\text{-month})} > 87\%$$

where $S_{6\text{-month}}$ is the probability that a subject remains free from Model 4798 lead related complications through 6 months since implant.

Endpoint Justification

The study primary safety endpoint is Attain Stability Quad MRI SureScan LV Lead (Model 4798) related complications. All reported system and procedure-related AEs will be reviewed by an event review committee for LV lead relatedness and severity (see Section 18.1).

Lead related complication free survival probability to evaluate lead safety performance is widely accepted across cardiac device manufacturers and in the medical literature. Current already market-released Quadripolar LV lead 6-month safety performance is summarized in Table 16. The population

performance of the Attain Stability Quad MRI SureScan LV Lead (Model 4798) is expected to be similar to the Medtronic Attain Performa Model 4298 lead.

Table 16: Safety Performance of Market Released Quadripolar Lead

	Medtronic Attain Performa	St. Jude Medical Quartet²²	Boston Scientific ACUITY X4²³
6-month LV Lead Complication Free Survival Probability Estimate	Model 4298 (Canted): 96.0% Model 4398 (Straight): 98.8% Model 4598 (S-shape): 96.2%	96% at 3 months	Straight: 96.5% Spiral: 98.5%

[figure not shown]
Statistical Analysis Methods

The primary objective will be analyzed using the time-to-first event Kaplan-Meier survival analysis method. A minimum number of subjects who have completed their 6-month post-implant visit will be required. Time 0 will be the day a subject undergoes the implant procedure of a Attain Stability Quad MRI SureScan LV Lead (Model 4798), which will be independent of success status of this implant procedure. Event date is the onset date of a subject's first complication that is related to the Attain Stability Quad MRI SureScan LV Lead (Model 4798) according to CEC adjudication. Subjects who undergo an Attain Stability Quad MRI SureScan LV Lead (Model 4798) implant attempt and do not experience any LV lead related complications, will be censored at the time of their last known exposure to the Attain Stability Quad MRI SureScan LV Lead (Model 4798) for the survival analysis. For any lost-to-follow up subject, the last contact date will be used as the censor date. The 1-sided 97.5% confidence limit lower bound for the survival probability at 6 months (183 days) will be calculated using the log-log survival function approach (Kalbfleisch and Prentice 2002).

Sample Size Consideration

The primary safety objective performance criterion is set to be identical to Medtronic's Attain Performa Clinical Study (IDE Number: G120213). Therefore, the sample size calculation assumptions are derived based on the Model 4298 lead study results. The Attain Performa Model 4298 lead reported a 6-month complication free survival probably of 96.0%, with 97.5% Confidence Lower Limit of 94.3% (PMA-s clinical report).

The binomial calculation (Z-test) is used for initial sample size estimation. In order to preserve the overall study power, a type II error less than 10% was used for the sample size calculation. A sample size of 170 subjects completing their 6-month visit achieves greater than 90% power to detect a difference of 7% using the one-sided binomial test. The target significance level is 0.025. These results assume that the population proportion under the null hypothesis is 87% with an expected value of 94% (Figure 5). To account for 15% attrition, the enrollment size for this objective is 200.

Figure 5: Primary Safety Objective Sample Size Consideration by Difference Performance Assumption**Determination of Patients / Data for Analysis**

All consented subjects who undergo an Attain Stability Quad MRI SureScan LV Lead (Model 4798) implant attempt will be included in the analysis cohort. If a patient experiences multiple Attain Stability Quad MRI SureScan LV Lead (Model 4798) implant procedures during the study, the analysis cohort will only consider the first procedure. In the event multiple complications occur, the survival analysis endpoint is reached when the first Attain Stability Quad MRI SureScan LV Lead (Model 4798) related complication occurs.

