Attain Stability Quad MRI SureScan LV Lead (Model 4798) capped or explanted without replacement with another Attain Stability Quad MRI SureScan LV Lead (Model 4798)

If the Attain Stability Quad MRI SureScan LV Lead (Model 4798) is capped or explanted without replacement while the subject is in the study, subjects will continue to be followed per their original follow-up schedule for safety monitoring until study closure. LV lead electrical testing and interrogation files will not be required at follow-ups for subjects without the full protocol required system implanted.

Explant of the Attain Stability Quad MRI SureScan LV Lead (Model 4798) and the Medtronic CRT-P or CRT-D device without replacement with another Attain Stability Quad MRI SureScan LV Lead (Model 4798) and Medtronic CRT-P or CRT-D device

Subjects who have their Attain Stability Quad MRI SureScan LV Lead (Model 4798) and Medtronic CRT-P or CRT-D device explanted without replacement during a system modification procedure should be exited from the study as soon as all system related and/or system modification procedure related AEs are resolved. If no system or procedure related AEs are present at the conclusion of such a system modification procedure, the subject should be exited immediately.

Medtronic CRT-P or CRT-D device explanted without replacement, Attain Stability Quad MRI SureScan LV Lead (Model 4798) remains implanted

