Subjects that are not anticipated to have an implant attempt (e.g. do not meet inclusion/exclusion criteria) must be exited from the study. Subjects that have a CRT system implant attempt, but who do not have an Attain Stability Quad MRI SureScan LV Lead (Model 4798) attempted (See Section 15.8.2.2 for definition) will be exited from the study following their procedure unless an Attain Stability Quad MRI SureScan LV Lead (Model 4798) attempt is scheduled. If this attempt is more than 30 days from the baseline assessment, verification of the baseline data must be completed prior to a subsequent implant attempt.

Subjects with an unsuccessful Attain Stability Quad MRI SureScan LV Lead (Model 4798) implant attempt will be followed at pre hospital discharge and one month unless there are ongoing implant related AEs (system- and/or procedure related), in which case they will be followed beyond one month until the implant related (i.e., system-, and/or procedure related) AEs have been resolved or are considered unresolved with no further actions planned. The subjects may be followed via a clinic visit or by phone contact. In geographies where the Attain Stability Quad MRI SureScan LV Lead (Model 4798) is market-released, subjects will be exited from the study after the assessment of implant procedure or CRT system related AEs if the initial attempt of one Attain Stability Quad MRI SureScan LV Lead (Model 4798) model was unsuccessful. The subject may undergo implant attempts with any market released LV lead that provides the best benefit to the patient, but data collection on these subsequent attempts will not be required as these subjects will be considered exited from the study.

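### The primary safety analysis counts complications after exposure ends but censors event-free subjects when it ends, so the Kaplan-Meier bound is slightly too low for the stated all-attempted probability

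*Protocol*

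**What the plan says.** Section 19.1.1 includes every consented subject with a Model 4798 implant attempt. Time 0 is the day of the procedure, "which will be independent of success status of this implant procedure". The event date is the onset of the first complication that the events committee judges related to the lead, and nothing restricts it to time with the lead in place. Event-free subjects "will be censored at the time of their last known exposure to the Attain Stability Quad MRI SureScan LV Lead (Model 4798". Subjects lost to follow-up are censored at a different date, that of last contact. The synopsis repeats these event and censoring rules, and both protocol versions in the file carry them.

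Follow-up continues after exposure ends. Under 15.16.2, subjects with an unsuccessful "implant attempt will be followed at pre hospital discharge and one month unless there are ongoing implant related AEs", in which case follow-up is longer. Under 15.14, if the lead alone is capped or explanted, "subjects will continue to be followed per their original follow-up schedule for safety monitoring until study closure". Section 15.8.2.2 states that a failed implant is not in itself an adverse event.

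The hypothesis concerns the probability that a subject stays free of lead-related complications through 6 months from implant. The objective is met if the lower one-sided 97.5% log-log bound at day 183 exceeds 87%.

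**The concern.** After a failed attempt the lead is out of the body on day 0, so the last known exposure is naturally read as day 0. A lead-related complication on day 10 in such a subject counts as an event. The same subject without a complication is censored at day 0, even if known to be event-free at one month. The rules also give an odd ordering: a failed attempt lost after day 5 is censored at day 5, while one who completes the one-month contact without an event is censored at day 0.

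Kaplan-Meier needs a single time-at-risk definition for events and censoring. With two, the curve estimates neither the all-attempted probability in the hypothesis nor a clean on-exposure probability. This bound decides the primary safety objective, and the date that drives it is undefined. The sensitivity analysis planned in 19.3.2 covers only the efficacy objectives.

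**Working it through.** **1. The plan's own figures.** 170/0.85 = 200 and 400/0.85 = 470.6, so 471; both agree with the protocol. For 87% against 94% at one-sided 0.025 with 170 subjects, a Z-test using the observed-proportion variance passes at 156 of 170 and has 91.2% power, matching the stated figure of more than 90%. None of this depends on the censoring rule.

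**2. Who is affected.**

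| Subject | If a complication occurs | If event-free, literal reading |
|---|---|---|
| Failed attempt | counts at onset | censored day 0, though generally followed to about one month |
| Lead explanted for a cause unrelated to the lead | counts at onset | censored at explant; if only the lead was removed, followed to study closure |
| Lead explanted for a lead-related adverse event | already an event (invasive intervention, Table 12) | not applicable |
| Lead capped | counts at onset | unclear: the lead is still in the body |

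Day-0 complications are unaffected, because the whole cohort is at risk then.

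**3. Worked case.** The protocol gives no failed-attempt rate for this lead, so these inputs are assumed except for N: 471 attempts; 24 failed (5%); 38 events (8%), 10 on day 0 and 28 by day 30; 2 of the 28 in failed attempts, leaving 22 event-free failed attempts.

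Bound: S^exp(1.96·√G/|ln S|), where G is the Greenwood sum.

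- Written rule: 461/471 = 0.97877 on day 0. The risk set is then 471 − 10 − 22 = 439, and 411/439 = 0.93622. S = 0.91634. G = 10/(461·471) + 28/(411·439) = 0.000201. Lower bound 88.68%.
- Failed attempts censored at day 30: S = 433/471 = 0.91932, the crude all-attempted proportion. G = 38/(433·471) = 0.000186. Lower bound 89.08%.
- Difference in the bound: 0.40 points.

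**4. Range at 471 attempts** (points by which the written rule lowers the bound; about 10% of failed attempts have a delayed event):

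| Failed attempts | 4% events | 8% events |
|---|---|---|
| 2.7% | 0.12 | 0.21 |
| 3% | 0.13 | 0.23 |
| 5% | 0.23 | 0.40 |
| 10% | 0.45 | 0.80 |

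The 2.7% row uses the only related figure in the protocol: 13 inabilities to implant in 490 procedures, from a single-centre series in Appendix 1 (Table 25).

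**5. Where the shift comes from.** Set delayed events in failed attempts to zero and keep the total unchanged. The shift does not vanish: it goes from 0.40 to 0.44 (5% failed, 8% events) and from 0.80 to about 0.9 (10% failed, 8% events). It therefore comes mainly from removing known event-free subjects before the later events are counted. A rough formula for the shift in S is late-event rate × (1/(1 − f) − 1), where f is the failed fraction. For 4% late events and f = 2, 5 and 10% it gives 0.08, 0.21 and 0.44 points.

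**6. Simulation** (1,500 runs per cell; 2% event-free explants; half of failed-attempt complications on day 0, the rest on days 1-30). Each cell gives the written rule / failed attempts censored at day 30 / everyone kept to day 183:

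| N, true S, failed | Mean lower bound (%) | P(pass) (%) |
|---|---|---|
| 471, 96%, 2% | 93.65 / 93.71 / 93.76 | 100 / 100 / 100 |
| 471, 96%, 10% | 93.25 / 93.49 / 93.73 | 100 / 100 / 100 |
| 471, 94%, 10% | 90.72 / 91.04 / 91.38 | 99.5 / 99.9 / 100 |
| 200, 94%, 10% | 88.82 / 89.20 / 89.61 | 78 / 84 / 91 |

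At the null (S = 87%) the written rule passed in 0.4-1.2% of runs, below the nominal 2.5%.

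**The case against.** Several counter-arguments stand in part.

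- **The computed shift is mostly not outcome-dependent censoring.** Correct, as step 5 shows. It largely reflects the difference between an on-exposure and an all-attempted risk set. The point remains because the stated hypothesis and cohort are all-attempted, and the event rule does not stop at end of exposure.
- **Last-contact censoring makes the test easier to pass.** True. It adds time with no lead in the body, when lead-related risk is low. That is the price of the estimand the protocol states, and the reason to report an on-exposure analysis beside it.
- **Less follow-up may be recovered than it seems.** Section 15.16.2 lets market-released geographies exit a failed attempt after adverse-event assessment, so last contact there may be close to day 0. Section 15.8.2.2 also allows a second Model 4798 attempt if the first caused no adverse event, which reduces final failures.
- **The SAP may define the term.** It is not shown and may do so. However, the protocol states the censoring rule itself and separates exposure from last contact. Section 15.16.2 likewise treats an attempt as exposure followed by a follow-up period.

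Two stronger inferences are not supported. A reader might infer that the rule could make an unsafe lead look safe; the shift is downward, so it cannot do that. A reader might also infer that the rule is likely to turn a pass into a fail. That needs a result close to 87%, whereas the planning values are 94% and 96%. The only noticeable loss of power is at 200 subjects, and the study plans up to 471.

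**Conclusion.** The point holds in limited form. Events and censoring are on different clocks, the censoring date is undefined, and read literally the curve does not estimate the stated 6-month probability for all attempted subjects. The lower bound is about 0.1-0.8 points too low at 471 attempts with 3-10% failed attempts and 4-8% events, and about 0.1-0.2 points at 2.7% failed. The bias is conservative, type I error is not inflated, and the pass probability at 471 stays at or above 99.5% in the simulated cases with true S of 94% or better. Failed attempts are the main affected group; explants for unrelated causes are secondary.

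The sizes rest on assumed rates of failed attempts, unrelated explants and delayed events, and on day 0 as the end of exposure after a failed attempt. The case for the change is a clearly defined primary estimate, not a threat to the conclusion.

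**What to change.** Use one time-at-risk rule for events and censoring in 19.1.1 and the synopsis. For the stated all-attempted estimand, the sentence could read: Subjects without a committee-adjudicated Model 4798-related complication are censored at their last adverse-event assessment or contact, whatever the implant outcome.

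Add a sensitivity analysis in which events and censoring both stop at end of exposure plus a fixed lag. Define end of exposure for a failed attempt, a capped lead and an explanted lead, and fix the lag before data freeze.

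The cost is one sentence plus a short sensitivity paragraph. No new data are needed, since last contact is already the censoring date for subjects lost to follow-up. The primary bound becomes slightly less conservative because lead-free time is included. Where a failed attempt is followed only to one month, the change recovers only part of the gap to full 183-day follow-up (for example 90.72% to 91.04%, against 91.38%, at 471 subjects, S = 94% and 10% failed).
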